### 6.3 Exploratory analyses

Unless specifically described, the following analyses will be analyzed similarly to the binary secondary outcomes, using a random effects logistic regression model with the cluster (health facility) and patient included as a random effect.

- % of children hospitalized among those referred for hospitalization during an initial consultation

Timing and method of measurement: Hospitalization determined by day 7 (6-14) phone call or home visit. Referral for hospitalization as determined by eCRF during the initial consultation.

- % of children referred for malnutrition management during the initial consultation

Timing and method of measurement: Referred for malnutrition as documented in eCRF during the initial consultation.

- % of children referred for or performed at the health facility tuberculosis screening during the initial consultation

Timing and method of measurement: As documented in the eCRF during the initial consultation.

- % of children tested for HIV during the initial consultation:

Timing and method of measurement: As documented in the eCRF during the initial consultation.

- % of children tested for any laboratory test during the initial consultation:

Timing and method of measurement: As documented in the eCRF during the initial consultation

- % of clinicians accepting the ePOCT+ testing, treatment, diagnosis, and management recommendations during the initial consultation

Timing and method of measurement: As documented in the eCRF of the intervention arm (ePOCT+) during the initial consultation

- % of children/caretakers seeking additional medications after the initial consultation

Timing and method of measurement: Asking caretakers if they procured additional medications for their child after the initial consultation by phone call or home visit at day 7 (6-14)

- Change in % of children with antibiotic prescribed over time

Timing and method of measurement: Antibiotic prescription as documented in the eCRF (control arm) / ePOCT+ tool (intervention) during the initial visit (day 0).

Analysis: Compare change in percentage of prescription from month to month, and from first half of the study compared to second half of the study for the intervention arm and the control arm, using the control arm as comparison to correct for seasonality, and presenting implementation team mentorship visits and combined implementation team and CHMT mentorship visits to contextualize changes. Independent sample t-test will be used to compare change in antibiotic prescription between intervention and control arm.

- Change in % of children with basic anthropometrics and clinical signs assessed (intervention arm only)

Timing and method of measurement: Measurement and documentation of individual basic measurements (height, MUAC, Temperature), and clinical signs (respiratory rate) as documented within the ePOCT+ tool during the initial assessment (Day 0).

Analysis: Descriptive statistics presenting change in documentation of basic measurements and clinical signs from month to month, and from first half of the study compared to second half of the study. Dates of implementation team mentorship visits and combined/supervised implementation team and CHMT mentorship visits and any changes in implementation strategy will also be presented to contextualize the changes. Subgroup analyses may be conducted for each intervention health facility.

- Change in % of cases managed using ePOCT+ over time (intervention arm only):

Timing and method of measurement: Uptake of ePOCT+ is defined as the use of the ePOCT+ tool to guide the clinical consultation including the decision on what treatment to prescribe during the initial consultation (Day 0).

Analysis: Descriptive statistics to present change in the proportion of health care workers' uptake from month to month, and from first half of the study compared to second half of the study will be presented. Dates of implementation team mentorship visits and combined/supervised implementation team and CHMT mentorship visits and any changes in implementation strategy will also be presented to contextualize the changes. Subgroup analyses may be conducted for each intervention health facility.

- Prognostic value of individual or combined predictors during the initial consultation to predict clinical failure/cure, hospitalization for more than one night and mortality (intervention arm)

Timing and method of measurement: Individual or combined predictors as documented in the eCRF during the initial consultation in the intervention arm. Clinical failure, hospitalization more than one night, and mortality assessed during the phone calls or home visit at day 7.

Method of analysis: ORs and 95% confidence intervals will be calculated using Pearson's chi-squared test or Fisher's exact test (two-tailed) for binary individual predictors. Initial selection of individual

predictors for the bivariate models will be determined by a group of clinical experts, with consideration of the algorithmic logic of the intervention tool to avoid circularity, and evidence on predictors already found to be prognostic. Multivariable ordinal logistic regression with lasso penalty will be used for covariate selection of the final model. Validity tests will be calculated including sensitivity, specificity, positive likelihood ratio, negative likelihood ratio, and area under the receiver operating characteristic. The dataset will be divided into a portion used for the derivation, and another portion for validation.

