Effect modification of the co-primary outcomes of antibiotic prescription and clinical failure will be performed in groups of patients where the highest reduction in antibiotic prescription is expected, and areas of extension of the content of the algorithm compared to the version tested in the previous ePOCT study. Effect modification by sex, age group (young infants ages 1 to 59 days, children aged 2 months to 5 years, and children aged 5 to 14 years), respiratory symptoms, fever without clinical source, gastrointestinal complaints (vomiting and diarrhea), skin problems, ear, nose and throat problems, will be assessed by incorporating an interaction between arm and the respective variable, acknowledging that power will be low. All models will be adjusted for clustering and the stratification factors (Kahan & Morris, 2012). Furthermore in order to adjust for potential imbalances in baseline characteristics between study groups, relevant baseline characteristics will be included as fixed effect variables in the final model. Baseline characteristic imbalance will be determined by consensus among the study analysis team.

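### The single-predictor prognostic odds ratios in SAP 6.3 ignore facility clustering and repeat records, so their intervals are too narrow when predictor and outcome both vary between facilities

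*SAP*

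**What the plan says.** SAP 6.3 opens with a default: "Unless specifically described, the following analyses will be analyzed similarly to the binary secondary outcomes", that is, "using a random effects logistic regression model with the cluster (health facility) and patient included as a random effect".

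The last item in the section studies predictors of clinical failure or cure, "hospitalization for more than one night and mortality (intervention arm" only). Its method is spelled out: "ORs and 95% confidence intervals will be calculated using" a Pearson chi-squared or two-tailed Fisher exact test, for each binary predictor. Candidates are not chosen by their intervals: "predictors for the bivariate models will be determined by a group of clinical experts", who also consider existing evidence. A penalised model follows: "Multivariable ordinal logistic regression with lasso penalty will be used for covariate selection of the final model". The data are then divided into derivation and validation portions. None of these steps mentions the facility.

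SAP 6.2 contains a general sentence, "All models will be adjusted for clustering and the stratification factors", placed with the effect-modification text.

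**The concern.** The default yields wherever a method is specifically described, and here one is. The sentence in 6.2 speaks of models, and a contingency-table test has nowhere to put a cluster term. Read as written, the rule treats children from the 20 intervention facilities as independent, and treats repeat records of one child as separate children. The patient random effect in the default shows that the SAP expects such repeats.

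If a predictor and the outcome both vary by facility, the unadjusted log odds ratio varies more than its naive standard error allows. The reported interval then overstates precision. What is at stake is the credibility of a published list of prognostic odds ratios. The protocol makes later interest in such predictors plausible: section 8.2 discusses predictors of severe outcome and of failure, and section 10.4.1 mentions better identification of patients with severe outcomes in Phase 1.

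**Working it through.** **Inputs from the documents.** 20 facilities in the intervention arm (SAP 3.1). Cluster size m = 900, outcome ICC 0.002, failure rate 3%, risk-ratio margin 1.3 (0.9 percentage points), 80% power, one-sided alpha 0.025 (SAP 3.3). No ICC is given for any predictor, so a range is assumed. None is given for hospitalisation or death.

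**Step 1: the plan's own figure.** This confirms how m and the ICC are used.
- Patients per arm without clustering: 2 × 0.03 × 0.97 × (1.960 + 0.842)² / 0.009² = 5,640.
- Design effect: 1 + 899 × 0.002 = 2.798.
- 5,640 × 2.798 = 15,781 patients, or 17.53 clusters of 900. Rounding up to 18 and adding one cluster for small-sample degrees of freedom gives 19 clusters and 19 × 900 = 17,100, as stated. With a t reference distribution, power is 78.7% at 18 clusters and 81.0% at 19.

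**Step 2: inflation for a patient-level predictor.** The figure 2.798 applies to a facility-level comparison. For a predictor x measured on each child, the variance of the unadjusted log odds ratio is inflated by about 1 + (m − 1) × ICC(x) × ICC(y). The true standard error exceeds the naive one by the square root R of this. The actual size of a nominal 5% test is 2 × [1 − Φ(1.96/R)].

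| Assumed predictor ICC | Inflation | R | Naive SE too small by (1 − 1/R) | Actual size |
|---|---|---|---|---|
| 0 | 1.00 | 1.00 | 0% | 5.0% |
| 0.05 | 1 + 899 × 0.002 × 0.05 = 1.09 | 1.04 | 4% | 6.0% |
| 0.10 | 1 + 899 × 0.002 × 0.10 = 1.18 | 1.09 | 8% | 7.1% |
| 0.30 | 1 + 899 × 0.002 × 0.30 = 1.54 | 1.24 | 19% | 11.4% |

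At a predictor ICC of 1 (a purely facility-level predictor) the inflation returns to 2.798 and R to 1.67.

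**Step 3: simulation check.** Settings: 20 facilities of 900, 3% failure, predictor prevalence 30% (assumed), true odds ratio 1, beta-distributed facility rates, ordinary large-sample interval, 6,000 runs per setting. Coverage of the nominal 95% interval:

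| Predictor ICC | Outcome ICC 0.002 | Outcome ICC 0.01 (assumed) |
|---|---|---|
| 0 | 94.8% | 94.8% |
| 0.02 | 94.8% | 93.5% |
| 0.05 | 94.1% | 90.0% |
| 0.10 | 93.3% | 84.9% |
| 0.20 | 91.0% | 76.8% |

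**Step 4: what the documents suggest about predictor clustering.** Protocol Table 1 gives malaria prevalence of 9.5% (Morogoro) and 4.0% (Mbeya), and section 4.2 plans 24 and 16 facilities. The weighted mean is 0.6 × 0.095 + 0.4 × 0.040 = 0.073. The between-region variance is 0.6 × 0.4 × 0.055² = 0.000726. Dividing by 0.073 × 0.927 = 0.0677 gives an ICC of about 0.011. Inflation is then 1 + 899 × 0.002 × 0.011 = 1.02, about 1% on the standard error. Variation between facilities within a region would add to this, but the documents do not quantify it.

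**The case against.** The best case on the other side is that this is an exploratory analysis in one arm and that the shortfall is small at the documents' ICC. That stands: over much of the plausible range, coverage stays within one or two points of 95%. Also, 900 is a planning figure. The SAP records lower enrolment than expected, and a smaller m shrinks the inflation.

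Several stronger readings are tempting, and the documents do not support them.

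- *All these intervals are too narrow.* Only where predictor and outcome both cluster by facility. A predictor spread evenly over facilities loses nothing.
- *The naive standard error is understated by 24% at a predictor ICC of 0.30.* The true one is 24% larger; the naive one is 19% too small.
- *Every other analysis in 6.3 has a facility random effect.* The change in antibiotic prescribing is compared by an independent-sample t-test, and the changes in measurements and in uptake of the tool are descriptive. The contrast is with the section's default only.
- *Weak predictors will be promoted into the Phase 2 algorithm.* No stated rule selects on an interval or p-value: experts choose candidates, the lasso selects and a validation portion follows. SAP 6.3 does not say these odds ratios feed Phase 2. Protocol 8.2 calls for expert review and retrospective testing, then a randomised sub-study where numbers allow.
- *These tests cannot give an interval.* Fisher's test can be inverted to give one. The SAP leaves the interval method unnamed, which is loose wording.
- *The ordinal model is wrong, or the data must be split by facility.* Failure, hospitalisation and death can form an ordered scale, though the SAP does not define the ordering. The unit of the split is also unstated, and splitting only 20 facilities costs precision. These are missing details and trade-offs.

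An unadjusted association across facilities is also a legitimate prognostic target, and a facility random intercept does not fully separate within- from between-facility association. The point here is therefore about the error bars, not about which association to estimate.

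**Conclusion.** The point holds in this conditional form. The method named for the single-predictor odds ratios omits facility clustering and repeat records, and it overrides the SAP's own default. At m = 900 and outcome ICC 0.002, intervals should be about 4%, 9% and 24% wider for predictor ICCs of 0.05, 0.10 and 0.30. Those predictor ICCs are assumptions, and applying 0.002 to every outcome is another. The formula and the simulation cover facility clustering only; repeat records were not quantified. If hospitalisation or death clusters more than overall failure, the loss is larger.

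This is a minor point. The co-primary results do not depend on it.

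**What to change.** Replace the chi-squared or Fisher sentence so that single-predictor odds ratios and 95% intervals come from the default random-effects logistic model with facility and patient effects. Alternatively, use cluster-robust intervals with a correction suited to 20 clusters. Either choice also names an interval method, which the present sentence lacks.

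The change is a line of SAP wording, with the same data. Its price is slightly wider intervals: close to none for predictors that do not cluster, and of the order shown above for those that do.

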If the microbiological surveillance in a few sentinel sites (see chapter 8.3) identifies a dengue outbreak, a dengue rapid test will be added to the "unspecific fever" branch of the algorithm and tested using the same study design as above. The modified "unspecific fever" branch including dengue testing will be implemented in all children if the clinical cure rate with this new branch is better (i.e. >30% decrease in the clinical failure rate) than that of children managed with the original "unspecific fever" branch will revert to the original version and the use of dengue rapid tests will be stopped.

Assessing the utility of typhoid rapid tests in high prevalence conditions:

If the prevalence of typhoid in febrile children is shown to be >10% in a certain area or time period (based on the microbiological surveillance data), using rapid tests, even with sub-optimal sensitivity and specificity as it is the case for now, could be beneficial from a clinical point of view. Indeed, with a pre-test probability of 10% and a positive likelihood ratio of 4 for the typhoid RDT, the post-test probability is 30%. The performance of the test can be enhanced by adding clinical predictors identified in previous studies in Tanzania (De Santis et al. 2017).

In this situation, a typhoid rapid test will be added to the "unspecific fever" branch of the algorithm and its clinical utility assessed using the same design as above. The new "unspecific fever" branch including the typhoid rapid test would be implemented in all children of the high prevalence area, if the clinical cure rate with the new branch is better (i.e. >30% decrease in the clinical failure rate) than that of the original branch. When typhoid prevalence decreases, the "unspecific fever" branch will revert to its original version.

Improving prediction of a severe clinical outcome:

If a combination of demographic, clinical and/or laboratory predictors, or a new POC test, seems to allow for better identification of children who will develop severe disease and thus be hospitalized secondarily or die, the benefit of adding an alert to HCWs in the algorithm, recommending them to refer the child to hospital, will be evaluated. If adding this alert allows to decrease mortality by at least 10%, it will be implemented for all children.

Adapting the algorithm to improve cure rates of children with chronic disease risk factors:

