## 3.3 Sample size

The primary analysis will evaluate whether the use of ePOCT+ for case management of sick children in PHC facilities 1) results in similar clinical cure at day 7 (non-inferiority analysis), as compared to routine care and 2) decreased antibiotic prescriptions (superiority analysis) at the initial consultation. The sample size was calculated for testing the non-inferiority of the clinical cure outcome, which will require a much larger sample size due to the rareness of clinical failure. In addition, the testing of differences in antibiotic prescription is conditional on satisfying non-inferiority in the clinical outcome. Assuming a failure rate (not being cured at day 7) of 3% in the control arm (corresponding to a 97% clinical cure rate), based on previous studies, the acceptable non-inferiority margin will be a risk ratio of 1.3. This corresponds to the upper bound of the difference in failure rate not exceeding 0.9% if the control group failure rate is 3%. We utilized a fixed risk ratio rather than an absolute risk difference to protect against potential unexpected event rates (Head et al. 2012).

We assumed a cluster size of 900 patients (average of 150 patients per month x 6 months) and an intraclass correlation coefficient of 0.002 in the clinical outcome based on similar studies. To have 80% power to detect a risk ratio 1.3, for a one-sided hypothesis test at alpha of 0.025, we would require 19 clusters and 17,100 patients per arm (total patients n=37,620 assuming 10% loss to follow-up), rounded to a total of 40 HFs and 40,000 patients. However, due to uncertainty regarding the assumptions of the sample size calculation and to capture a wider more representative range of conditions, we will continue recruitment for Phase 1 for a minimum of 6 months.

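### SAP 6.3 asks about predictors of failure, hospitalisation and death, but one ordinal lasso would answer mainly for failure; a separate severe-outcome model and accuracy per outcome are needed

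*SAP*

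**What the plan says.** The last item of SAP 6.3 (Exploratory analyses) assesses the prognostic value of predictors recorded at the initial consultation "to predict clinical failure/cure, hospitalization for more than one night and mortality (intervention arm" only). The steps it sets out are:

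- **Univariable.** Odds ratios by Pearson's chi-squared or Fisher's "exact test (two-tailed) for binary individual predictors". Candidates are chosen by clinical experts. The SAP does not say which of the three outcomes these odds ratios use.
- **Multivariable.** "Multivariable ordinal logistic regression with lasso penalty will be used for covariate selection of the final model". The final model is singular. The ordinal levels are not listed, and proportional odds is neither stated nor checked.
- **Accuracy.** "Validity tests will be calculated including sensitivity, specificity, positive likelihood ratio, negative likelihood ratio, and area under the receiver operating characteristic". These measures need a two-category outcome, and none is named.
- **Validation.** "The dataset will be divided into a portion used for the derivation, and another portion for validation". The fraction is not given.

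SAP 6.3 opens with a default of random-effects logistic regression for analyses not specifically described. This analysis is specifically described, so the default does not clearly supply separate binary models.

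Under the definitions that follow SAP 6.1.2, only a non-referred secondary hospitalisation automatically makes a child a clinical failure.

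**The concern.** The three outcomes differ greatly in rarity. A proportional-odds model gives a predictor one odds ratio, taken as equal at cured v failure or worse, at hospitalised or worse, and at death. When nearly all non-cured children are mild failures, that odds ratio is close to the one for failure v cure. Two errors can follow. A predictor that acts only on severe outcome is diluted and may be dropped. A predictor that acts only on mild failure is kept, with an odds ratio that the model also applies to death.

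The ordering is a second difficulty. A child referred at the initial consultation can be hospitalised for more than one night and be reported as cured or improved by day 7. That child is cured on one outcome and severe on another, so the three outcomes do not form a ladder unless the SAP defines one.

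What is at stake is whether the analysis answers its own question on hospitalisation and death. Protocol 8.2 also takes an interest in "better identification of children who will develop severe disease and thus be hospitalized secondarily or die".

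**Working it through.** **1. Size of the data set.** The SAP gives no sample size for this analysis, so the trial's size sets the number of events. SAP 3.3: "Assuming a failure rate (not being cured at day 7) of 3% in the control arm" and "we would require 19 clusters and 17,100 patients per arm".

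- Non-inferiority on the difference scale: n = 2 × 0.03 × 0.97 × (1.960 + 0.842)² / 0.009² ≈ 5,640 per arm.
- Design effect: 1 + 899 × 0.002 = 2.798, giving about 15,780 per arm, or 17.5 clusters of 900, so 18.
- With t quantiles, or one added cluster, this becomes 19 clusters = 17,100, as stated. The total is 2 × 17,100 × 1.1 = 37,620, as stated.

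**2. Assumptions.** The documents give no hospitalisation or death rates. I take the 3% failure rate for the intervention arm, place all severe outcomes (hospitalised or died) inside it, and vary their share. Predictor prevalence is 10%. Clustering is ignored.

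**3. Where the information lies.** At each cut it is roughly proportional to p(1 − p). With 0.55% severe, including 0.05% deaths:

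- failure or worse: 0.03 × 0.97 = 0.0291
- hospitalised or worse: 0.0055 × 0.9945 = 0.0055
- died: 0.0005 × 0.9995 = 0.0005

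The shares are 83%, 16% and 1%. Over severe rates of 0.22% to 1.3%, the first cut holds 92% down to 65%, and the death cut 1% to 7%.

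**4. The common odds ratio.** The odds ratio at the cured/failure cut is (mild rate × its multiplier + severe rate × its multiplier) / 0.03. At 0.55% severe the mild rate is 0.0245:

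- severe-only odds ratio 3: (0.0245 + 3 × 0.0055) / 0.03 = 1.37
- mild-only odds ratio 2: (2 × 0.0245 + 0.0055) / 0.03 = 1.82

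A large-sample proportional-odds fit gives almost the same values:

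| Severe rate (deaths) | Share of failures | Severe-only OR 3: cured/failure cut | Severe-only OR 3: common OR | Mild-only OR 2: cured/failure cut | Mild-only OR 2: common OR |
|---|---|---|---|---|---|
| 0.22% (0.02%) | 7% | 1.15 | 1.15 | 1.93 | 1.92 |
| 0.55% (0.05%) | 18% | 1.37 | 1.38 | 1.82 | 1.81 |
| 1.1% (0.1%) | 37% | 1.73 | 1.76 | 1.63 | 1.62 |
| 1.3% (0.3%) | 43% | 1.87 | 1.89 | 1.57 | 1.56 |

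For the mild-only predictor the true odds ratio for death is 0.97 to 0.98 throughout.

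**5. Lasso selection.** Simulated with a derivation set of two thirds (11,400, assumed), 16 binary predictors, penalty chosen by AIC, 150 runs:

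| Predictor | Severe rate | Ordinal lasso keeps | Binary lasso on hospitalised-or-died keeps |
|---|---|---|---|
| Severe-only OR 3 | 0.55% | 65% | 96% |
| Severe-only OR 3 | 0.22% | 32% | 69% |
| Mild-only OR 2 | 0.55% | 96% | 11% |
| Mild-only OR 2 | 0.22% | 98% | 17% |
| Death-only OR 5 | 0.55% / 0.22% | 22% / 18% | 34% / 21% |
| Noise | 0.55% / 0.22% | 22% / 20% | 14% / 15% |

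**6. Single-predictor tests.** Full 17,100, likelihood-ratio tests at 5%, severe rates 0.3% / 0.5% / 1.0%, ranges over repeated simulations:

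- Severe-only OR 3: ordinal detects 29-31% / 50-55% / 95-97%; binary severe model 86-88% / 96-97% / 99-100%.
- Acting on both (OR 1.5 mild, 2 severe): ordinal 90% / 89-95% / 95-98%; binary severe model 41-44% / 54-64% / 86-93%.

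**7. Deaths.** 17,100 × 0.0002 ≈ 3; × 0.001 ≈ 17; × 0.003 ≈ 51.

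**The case against.** The strongest objection is that SAP 6.3 never says proportional odds. A partial or non-proportional ordinal model would not force one odds ratio on every cut. This stands: the harm depends on the form fitted, and the SAP's silence is itself part of the gap.

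Second, the ordinal model is sometimes the better one. For a predictor that raises both mild and severe outcomes it has clearly more power (step 6), so replacing it outright would lose real predictors. This also stands, and it argues for adding a model. Even then the common odds ratio (about 1.5 to 1.7) follows the mild effect and understates the severe odds ratio of 2.

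Third, the nesting in step 2 may be wrong. Hospitalisation of more than one night is not limited to non-referred admissions. If referred admissions are ranked as severe, the severe share rises towards the range where the ordinal model performs well. That is fair, and it shows why the levels need defining.

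Fourth, the univariable odds ratios, the expert choice of candidates and the validation portion could expose a predictor unrelated to severe outcome. They would do so only if reported by outcome, which the SAP does not say.

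A reader might also infer that a Phase 2 referral alert will rest on this model. The documents do not say so. Protocol 10.4.1 describes a separate, clinician-led route to modifications. Protocol 8.2 requires expert review and retrospective testing, a randomised sub-study where numbers allow, and a fall in mortality before an alert is adopted.

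**Conclusion.** The plan poses a question about three outcomes and names one selection step that, in its standard form, answers chiefly for clinical failure. Predictors of severe outcome alone are diluted. They are often dropped when severe outcomes are about one fifth of failures or fewer (kept in 32% to 65% of runs, against 69% to 96% with a severe-outcome model), and usually found when the share is one third or more. Predictors of mild failure alone are kept almost always, with a common odds ratio of 1.56 to 1.92 that would be read across to death. These sizes rest on proportional odds, 3% failure, assumed severe rates, 10% predictor prevalence, an assumed two-thirds split and no clustering. SAP 3.4 reports lower enrolment than expected, so actual event counts may be smaller.

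A reader might go further and conclude that severe-disease predictors will be missed, or that the ordinal model is wrong in both directions and should go. The documents do not support that. The model form and event rates are not stated, a lasso selects coefficients and tests no null, and predictors acting on both levels favour the ordinal model.

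The analysis is exploratory, in one arm, and touches neither co-primary outcome. The point is a cheap improvement that should be made before the prognostic analysis is run.

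**What to change.** Amend the last item of SAP 6.3 as follows:

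- Keep the ordinal lasso if wanted, but list its levels, say where a child who was referred, hospitalised and then cured is placed, and report cut-specific (partial proportional-odds) coefficients.
- Add a separate penalised binary model for the severe outcome: hospitalised more than one night or died.
- Report univariable odds ratios, sensitivity, specificity, likelihood ratios and AUROC separately for clinical failure and for severe outcome.
- Base any statement about severe outcome on the severe-outcome model.

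The cost is SAP wording and one further model fit on data already collected. The severe-outcome model has few events: in a derivation set of 11,400, about 25 at 0.22% and 63 at 0.55%. Its intervals will be wider and it may retain fewer predictors. It has less power than the ordinal model for predictors that act on both mild and severe outcomes, which is the reason to report both. It barely helps for death alone: with roughly 3 to 17 deaths expected at 0.02% to 0.1%, predictors of death only remain largely undetectable by either model, and the report should say so.
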